2. We will minimize the risk of potential suicidal or homicidal ideation by instituting the proper procedures for protecting the safety of participants and others, which we have applied extensively in our prior and ongoing research at the RIDOC. During incarceration, Per RIDOC policy, their standards for mandatory reporting of suicide risk (i.e., breaking confidentiality to report suicide risk) specify that we are required to report anyone who has had suicidal ideation within the past 24 hours (as determined through query and follow-up for an endorsement of any score > 0 on item 9 of the PHQ-9 or reporting of any current desire to hurt oneself to any member of the research staff). We will follow this RIDOC policy, per their requirements for researchers conducting human subjects research with any of their facilities. If the participant reports this level of SI within the past 2 weeks, but not in the 24 hours prior to the assessment, the RA will notify one of the PIs (both of who are licensed psychologists) or their covering licensed clinician who will make a clinical determination if further referral or action is needed, and a voluntary referral will be offered. Participants meeting the prison's SI mandatory reporting criteria (or those who elect the voluntary referral) will be referred to a prison mental health clinician for evaluation, who will follow prison procedures. When confidentiality must be broken due to a RIDOC mandatory report, the research staff member will report the information to a social worker, a nurse, and/or the highest ranking person available (i.e. Captain, Lieutenant, Correctional Officer, etc.). We will prioritize reporting to a medical staff member first, but will report to the highest ranking person available if a medical staff member is unavailable at the time of the report. Standard prison procedures include: (1) checking with the prison's behavioral health department to see if the person has already been flagged as having SI; (2) having a licensed mental health clinician check in with the person and do a suicide risk evaluation; and/or (3) if needed, putting the person on psychiatric observation within the prison. If the prison mental health professional determines that someone's risk has gone down, that person will leave psychiatric observation and return to the general population. All of these procedures are set and executed by the prison, which follows its own ethical and legal requirements. We will clearly describe this in our consent form. Homicidal risk will be defined by reporting any desire to hurt another person, including any member of the study staff. Standard mandatory reporting procedures (e.g., contact prison mental health staff), per RIDOC policy, will be followed.

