3. We will minimize the risk of distress by informing all participants that they do not have to answer questions that they find too distressing and will be reminded that they can discontinue participation at any time. Focus groups will be led by a licensed clinician (Drs. [name], [name], and/or one of the study Co-Is) to help facilitate the stabilization and referral process if participants who decompensate during study procedures. In the pilot RCT, clinical backup will be provided during all assessments and intervention sessions by a licensed clinician to help facilitate the stabilization and referral process for participants who decompensate during study procedures. The need for additional services will also be monitored during each clinical (assessment or intervention) contact. Participants will be formally assessed at 4 time points (baseline, 5 weeks, 10 weeks, 18 weeks). Incarcerated participants who manifest significant psychiatric symptomatology (i.e., psychosis or mania per the MINI Neuropsychiatric Interview) will be referred to appropriate clinical prison staff for evaluation, per RIDOC policy, following the same procedures for participants who report significant homicidal ideation or suicide risk (as described above). For any assessments in the community (in the rare event that a participant is released from prison prior to study completion), a licensed clinician (the MPIs or their covering clinician) will be available at all times to provide clinical coverage. Research staff will notify the licensed clinician if there are any safety concerns

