7.2 Specification of Safety Parameters

Safety issues will be minimal in Phase 1 given that participation involves only a single focus group, no yoga classes, and no formal assessment of suicidality. However, should an issue arise (e.g., a voluntary report of suicide ideation), staff would manage it in the same way that they would manage it in Phase 2.

Please see Table 4 for a summary of safety issues, how they are assessed, when they are assessed, and relevant staff actions.

Table 4. Assessment and Management of Safety Issues, Summary, Phase 2

Safety Issue	How assessed	When Assessed in Phase 2	Relevant Research Staff Actions
Suicide or homicidal ideation	PHQ-9 Participant report to research staff	BL, wk5, wk10, wk18 Any point	Immediate clinical assessment as described in DSMP
Injuries due to yoga	Structured self-report	Weekly during first 10 weeks	Follow until resolution; may result in changes to yoga instructor manual
Other AEs	SAFTEE Participant report to research staff	BL, wk5, wk10, wk18 Any point	If related to study participation, follow resolution; potential changes to procedures particularly if AE is also unexpected

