Suicide or homicide ideation. Given that participants will have risk factors for suicide or homicide (e.g., a mental health diagnosis, incarceration), some participants may experience suicide ideation or behavior in the course of study participation. During incarceration the RIDOC standards for mandatory reporting of suicide risk specify that we are required to report anyone who has had suicidal ideation within the past 24 hours (as determined by participant reporting of any current desire to hurt oneself to any member of the research staff). If the participant reports this level of SI within the past 2 weeks, but not in the 24 hours prior to the assessment, a voluntary referral will be offered. Participants meeting the prison's SI mandatory reporting criteria (or those who elect the voluntary referral) will be referred to a prison mental health clinician for evaluation, who will follow prison procedures. Standard prison procedures include:

(1) checking in the prison's electronic medical record to see if the person has already been flagged as having SI; (2) having a licensed mental health clinician check in with the person and do a suicide risk evaluation; and/or (3) if needed, putting the person on psychiatric observation within the prison. If the prison mental health professional determines that someone's risk has gone down, that person will leave psychiatric observation and return to the general population. All of these procedures are set and executed by the prison, which follows its own ethical and legal requirements. We will clearly describe this in our consent form. Homicidal risk will be defined by reporting any desire to hurt another person, including any member of the study staff. Standard mandatory reporting procedures (e.g., contact prison mental health staff) will be followed.

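### Protocol 7.1 and DSMP section 5 describe the same suicide-risk reporting standard differently, and Table 4 sends staff to the version that lacks the clinician notification

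*Combined protocol and SAP*

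**What the plan says.** Three places set out what staff do about suicidal ideation in an incarcerated participant.

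**Protocol 7.1, Protection Against Risks, item 2.** Ideation in the past 24 hours must be reported to the prison. It is identified "as determined through query and follow-up for an endorsement of any score > 0 on item 9 of the PHQ-9". The alternative route is a participant telling research staff of a present wish for self-harm. If the ideation falls in the past 2 weeks but not the past 24 hours, the RA notifies a PI or a licensed clinician providing cover. That person "will make a clinical determination if further referral or action is needed, and a voluntary referral will be offered".

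**DSMP section 5, Expected Risks, suicide or homicide ideation.** The same prison standard and the same 24-hour window apply, but ideation is identified "as determined by participant reporting of any current desire to hurt oneself to any member of the research staff". For the 2-week period the only stated step is the offer of a voluntary referral.

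**Protocol 7.2, Table 4.** The assessment methods are the PHQ-9 (baseline and weeks 5, 10 and 18) and participant report at any point. The staff action is "Immediate clinical assessment as described in DSMP".

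**The concern.** Both texts claim to state one external standard, set by the prison system, so at least one of them is incomplete. The difference matters in practice because of the direction of the cross-reference. Table 4 is the summary that an RA is likely to consult. It names the PHQ-9 and then sends the RA to the DSMP for the action. In the DSMP text available, the RA finds no rule for a non-zero item 9 answer. For ideation in the 2-week period, the RA finds no instruction to contact a clinician.

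What is at stake is a participant-safety step in a population that the protocol itself describes as carrying risk factors for suicide. Under the DSMP wording, a participant in the 2-week period who declines the voluntary referral gets no clinician review under that rule. Under the protocol wording, a PI or covering clinician has already been told and has made a judgement.

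**Working it through.** No arithmetic applies, so the check sets the texts side by side.

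| Element | Protocol 7.1, item 2 | DSMP section 5 | Table 4 |
|---|---|---|---|
| Identifying ideation in the past 24 hours: PHQ-9 item 9 | Yes, any score above 0, with query and follow-up | Not mentioned | PHQ-9 listed as a method |
| Identifying ideation in the past 24 hours: report to staff | Yes | Yes | Listed as a method |
| Past 2 weeks, not past 24 hours: RA notifies PI or covering clinician | Yes | Not mentioned | Action deferred to DSMP |
| Past 2 weeks, not past 24 hours: clinical determination | Yes | Not mentioned | Action deferred to DSMP |
| Past 2 weeks, not past 24 hours: voluntary referral offered | Yes | Yes | Action deferred to DSMP |

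1. *Identification.* The protocol has two routes, joined by an explicit alternative: item 9 followed by a query, "or reporting of any current desire to hurt oneself to any member of the research staff". The DSMP has one. Reading the rest of the DSMP for any mention of the PHQ-9 finds none.

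2. *Action in the 2-week period.* The protocol has three steps: notification, determination and offer. The DSMP has one, the offer.

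3. *Does Table 4 close the gap?* Only in part. It keeps the PHQ-9 as an assessment method ("PHQ-9 Participant report to research staff"), so the item would still be collected and seen. For the action, however, it cites an immediate clinical assessment described in the DSMP. For an incarcerated participant in the 2-week period, DSMP section 5 describes no such assessment. Immediate contact with a study clinician appears there only for participants who have been released.

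4. *Does other DSMP text restore the missing step?* Two places could. DSMP 1.2 says the DSMP will adhere to the IRB-approved protocol. That is a general statement; it does not supply the missing wording, and Table 4 points the other way, from protocol to DSMP. The paragraph on distress in DSMP section 5 provides licensed-clinician backup during assessments and sessions and tells staff to notify the clinician of safety concerns. The backup is for participants who decompensate, and the notification sentence directly follows one about assessments in the community. Neither states a rule for item 9 or for ideation in the 2-week period in prison.

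5. *After release.* The protocol and the DSMP both require immediate contact with a clinician when any suicidal ideation is found in standard assessments. The gap in action is therefore confined to participants who are still incarcerated.

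**The case against.** The strongest reply is that the DSMP is a shorter account of the same procedure and not a rival one. Both texts share the 24-hour window, the report-to-staff route and the voluntary referral. The PHQ-9 is a self-report form completed in a study assessment, so participant reporting in the DSMP could be read to include an item 9 answer. Table 4 names the PHQ-9 itself and defers to the DSMP for the action only, so an RA would have to overlook both 7.1 and Table 4 to ignore a non-zero answer.

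Much of this stands. For identification, the gap is an omission and not an opposing instruction. The reading of participant reporting is arguable, although the protocol lists the two routes separately. None of it restores the clinician notification in the 2-week period, which is the step most likely to be lost.

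A reader might also infer more than the documents support:

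- *That any item 9 score above 0 is itself the reporting criterion.* It is not. The score opens a query, and the criterion is ideation in the past 24 hours.
- *That the rule on referral for psychosis or mania ("psychosis or mania per the MINI Neuropsychiatric Interview") conflicts with Table 3, which schedules the MINI at baseline only.* The text mentions four assessments but does not say that the MINI is repeated. A referral based on the baseline MINI fits Table 3 and the exclusion criterion in section 4.3.
- *That 3 follow-up PHQ-9s x 40 participants = 120 measures the problem.* This is a ceiling on follow-up forms. It assumes full retention, against targets of 80% at week 10 (0.80 x 40 = 32) and 70% at week 18 (0.70 x 40 = 28). It includes post-release assessments, leaves out baseline, and says nothing about how many answers would be non-zero.
- *That the two texts would distort a trial result.* No planned outcome counts referrals or safety actions. The safety target in section 9.5.1 concerns related serious adverse events and injuries.

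**Conclusion.** The inconsistency is real and should be corrected. For incarcerated participants, DSMP section 5 omits one of the protocol's two routes for identifying ideation in the past 24 hours. It also omits two of the three steps for ideation in the past 2 weeks. Table 4 directs staff to the DSMP for the action. Staff who follow it could therefore leave out a clinician notification that protocol 7.1 requires.

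The number of participants affected cannot be derived: the documents give no expected rate of item 9 endorsement or of ideation in either period. The point does not touch the feasibility and acceptability analyses. It rests on the DSMP text as available for review and on Table 4 being used as written. No view is taken on which rule is right.

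**What to change.** Reconcile protocol 7.1 item 2, Table 4 and DSMP section 5 so that all three state one identical way of identifying ideation and one identical action for each recall period (past 24 hours; past 2 weeks but not past 24 hours). Table 4 should cite a section that contains the action it names. Which rule applies is for the sponsor and the prison authority.

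Two neighbouring differences can be settled in the same pass. The DSMP discontinues participants hospitalized over suicidality, a provision found neither in the matching paragraph of protocol 7.1 nor in the list in section 8. The first prison check also differs: it goes through the behavioral health department in the protocol and the electronic medical record in the DSMP.

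The cost is a text amendment to the protocol and the DSMP, with its usual approvals, and staff training on the agreed wording. No change to design, sample size or analysis is needed.

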For all follow-up assessments, research staff will make every effort to conduct the assessment within one week before or one week after the exact due date of the assessment. However, because all data can be analyzed with modern statistical methods regardless of whether it was collected inside that window, RAs will still collect data if possible even if it is later than that two-week window. We will record optimum date for the assessment as well as the actual date of the assessment.

Participants will complete a brief assessment after each class that they attend.

In addition, all participants will be assessed at: baseline, 5 weeks (mid-intervention), 10 weeks (post-intervention), 14 weeks (yoga group participants only), and at 8 week follow-up. In addition to demographics, we will assess acceptability of the intervention conditions, safety of the yoga condition, anger and aggression, secondary outcomes (depression and anxiety symptoms, general functioning), potential intervention mechanisms of action (anger rumination, decentering, impulsivity), and other descriptive characteristics (trauma history, treatment utilization, physical activity levels).

In the event that a participant is released back into the community before they complete all of their study assessments, we will complete them in the community. We will aim to complete all of these follow-up assessments by telephone. However, there may be some circumstances that might make it difficult for a participant to complete the follow-up assessment by telephone (e.g., limited phone minutes, enrollment in a residential treatment program). In such cases, we will complete the follow-up assessment in person in our offices at Brown University or in the facility where the participant is located (e.g., residential treatment facility, with facility approval). Additionally, if a participant is transferred to another facility at RIDOC, we will complete their assessments at the other facility (e.g., Men's Maximum Security) with RIDOC approval.

Please see table 3 for a list of all assessments to be completed at each visit.

6.2.7 Completion/Final Evaluation - Phase 2

Even if prisoners drop out of study treatment, we will attempt to collect data at all assessment points if prisoners agree to it.

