
Given study inclusion criteria, we think it unlikely that anyone will be released into the community while participating in the study. However, we do have procedures in place for people post-release. During the post-release period, definitions of suicide risk, and homicide risk will be the same those described above; however, we will rely upon our standard study procedures (vs. RIDOC mandatory/ voluntary reporting criteria) to facilitate clinician referral and safety assessment, as needed. If any study staff member identifies an individual who reports any suicidal or homicidal ideation in the course of standard assessment procedures, the staff member will immediately contact [name] or [name] (or the licensed covering clinician). The covering clinician will evaluate the participant over the telephone or in person. First, they will conduct a suicide and homicide risk assessment to determine whether it is necessary to take immediate action to prevent the participant from causing harm to self or others. If needed, actions that the covering clinician may take include escorting the person to the emergency Patient Assessment Service (PAS) at Butler Hospital (if the person is in our offices), having a family member transport the person to Butler Hospital or another hospital, or sending an ambulance so that the individual may be evaluated for inpatient psychiatric hospitalization.

A participant who has undergone a suicide or homicide risk assessment may continue to participate in the study unless the study PIs, in concert with the participant's healthcare providers, deem study participation to increase risk for this particular participant.

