8. INTERVENTION DISCONTINUATION

Prisoners will be discontinued from an intervention in the following circumstances:

- If the prisoner or prison staff does not believe it is in the best interest of the prisoner to continue. As soon as an MPI is informed of this, study staff will speak with the participant about discontinuation, if possible.
- If a prisoner chooses to discontinue attendance.
- If one of the MPIs, in consultation with the relevant instructor, finds the prisoner to be so disruptive to the rest of the class that he/she has a repeated and substantive negative impact on the other participants.
- If a prisoner is released from prison unexpectedly.
- If a prisoner exhibits inappropriate behavior towards study staff.

Participants will continue with subsequent assessments if they are willing to do so. Assessment schedule and assessments used will not change.

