9.5 Outcomes

9.5.1 Primary Outcome.

The primary outcomes are acceptability, feasibility, and safety.

Target treatment development outcomes. We monitor treatment development outcomes (see Table 6) throughout the trial. Target outcomes were chosen on face validity, clinical experience, and, when available, relevant clinical literature. At 3 time points throughout the RCT (i.e., after enrolling 10, 20, and 40 participants), the scientific team will convene to discuss how our actual procedural outcomes compare to the target outcomes. Discrepancies will result in: 1) investigation (using qualitative or other data) of the reason for the failure to meet this outcome; and 2) discussion amongst the research team. Depending on the nature of the discrepancy, we may modify recruitment procedures, assessment procedures, instructions to participants, instructor training procedures, or other aspects of the trial. Ultimately, failure to meet these outcomes could result in a decision not to write a grant proposal for a large-scale RCT; in other cases, it may inform the design of a subsequent RCT.

Primary data analyses will be focused on feasibility and acceptability (see Table 6) using intent-to-treat population. Study measures and endpoints will continue to be collected for all enrolled participants if they are willing, even in the event of premature discontinuation of the study intervention.

Table 2. Target Outcomes

Description (Assessment method)	Target
Feasibility and Acceptability-- Hatha yoga, Health education	
Acceptability (qualitative interview)	Most feedback positive; few substantive negative comments. Negative comments used to enhance procedures.
Credibility at baseline (CEQ)	Average > 50 (i.e., midpoint score between low and high credibility) on subscale
Expectancy at baseline (CEQ)	Average > 50 (i.e., midpoint score) on subscale
Program satisfaction (CSQ-8)	Average total score > 24
Home practice (homework questionnaire)	70% of yoga participants engage in practice at least 2 times per week for 6/10 weeks.
Class attendance	70% of all participants complete 6/10 classes in the RCT
Instructor adherence (Adherence measures)	Yoga instructors and HE instructors achieve at least 80% adherence on a random subset of classes taught
Class size	70% of classes have 4 or more participants.
Safety	
Adverse events (SAFTEE; injuries due to yoga)	No serious adverse events or injuries that are possibly, probably, or definitely related to study participation.

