Given study inclusion criteria, we think it unlikely that anyone will be released into the community while participating in the study. However, we do have procedures in place for people post-release. During the post-release period, definitions of suicide risk, and homicide risk will be the same those described above; however, we will rely upon our standard study procedures (vs. RIDOC mandatory/voluntary reporting criteria) to facilitate clinician referral and safety assessment, as needed. If any study staff member identifies an individual with significant clinical deterioration or who report any suicidal or homicidal ideation in the course of standard assessment procedures, the staff member will immediately contact [name] or [name] (or the licensed covering clinician). The covering clinician will evaluate the participant over the telephone or in person. First, they will conduct a suicide and homicide risk assessment to determine whether it is necessary to take immediate action to prevent the participant from causing harm to self or others. If needed, actions that the covering clinician may take include escorting the person to the emergency Patient Assessment Service (PAS) at Butler Hospital (if the person is in our offices), having a family member transport the person to Butler Hospital or another hospital, or sending an ambulance so that the individual may be evaluated for inpatient psychiatric hospitalization.

A participant who has undergone a suicide or homicide risk assessment may continue to participate in the study unless the study PIs, in concert with the participant's healthcare providers, deem study participation to increase risk for this particular participant. Participants who are hospitalized due to concerns about suicidality will be discontinued from the study.

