3.4.6 Reporting of Pregnancy

Because prenatal yoga is considered safe and is recommended for pregnant women, and the yoga intervention that we intend to provide will not be strenuous, we have no reason to believe that it will be harmful to pregnant women. However, if a woman becomes pregnant during the course of the study, we will ask her to stop participating in the yoga intervention. With her permission, we will continue assessments with her on the usual assessment schedule.

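### The DSMP takes participants hospitalised for suicidality out of the study, while the protocol keeps assessing willing participants after the intervention stops; align the two texts (low priority)

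*Combined protocol and SAP*

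**What the plan says.** DSMP section 5, in the paragraphs on suicide or homicide ideation, sets a fixed consequence: "Participants who are hospitalized due to concerns about suicidality will be discontinued from the study". It makes no provision for later assessments.

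The protocol separates leaving the intervention from leaving the study, in three places:

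- Section 6.2.7: "Even if prisoners drop out of study treatment, we will attempt to collect data at all assessment points if prisoners agree to it".
- Section 8, which concerns discontinuation from an intervention: "Participants will continue with subsequent assessments if they are willing to do so". The schedule and instruments stay the same. Hospitalisation for suicidality is not among the listed reasons.
- Section 9.5.1: "Study measures and endpoints will continue to be collected for all enrolled participants if they are willing", including when the intervention ends early.

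Section 9.3 specifies an intent-to-treat population with all available data. Section 7.1 has a paragraph that largely matches the DSMP one. It includes the rule beginning "A participant who has undergone a suicide or homicide risk assessment may continue to participate in the study unless the study PIs", under which the principal investigators, with the participant's healthcare providers, may end participation that raises risk. It does not include the hospitalisation sentence.

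Where the DSMP means only the intervention, it says so. Under its pregnancy rule (section 3.4.6) yoga stops, but "With her permission, we will continue assessments with her on the usual assessment schedule".

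**The concern.** Both texts are current, and they give different instructions for the same participant. Someone working from the DSMP would cancel the remaining visits; someone working from the protocol would keep them.

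The visits at risk are not incidental. Protocol Table 4 names the PHQ-9 as the scheduled check for suicidal ideation and the SAFTEE as the scheduled inquiry about other adverse events. Ending both after a suicidality admission removes structured follow-up from someone just identified as at risk. It also makes missing data depend on a clinical event close to depression, a secondary outcome. The link to anger on the NAS is less direct. Missingness of this kind is plausibly informative, though the documents do not demonstrate it, and it sits badly with an intent-to-treat analysis of all available data.

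**Working it through.** The plan has no figure to reproduce here: protocol section 9.1 says the trial is not powered to compare treatments. The check is a comparison of texts, followed by arithmetic to size the effect.

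**1. The texts side by side**

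| Source | What ends | Assessments afterwards |
|---|---|---|
| DSMP 5 | The study | None provided for |
| Protocol 6.2.7 | Study treatment | Attempted at every time point, with agreement |
| Protocol 8 | The intervention; this trigger not listed | Continue if willing, schedule unchanged |
| Protocol 9.5.1 | The intervention | Continue for all enrolled, if willing |
| Protocol 7.1 | Participation, by investigator judgement of risk | Not stated; no hospitalisation rule |
| DSMP 3.4.6 (pregnancy) | Yoga | Continue, with permission |

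DSMP section 1.2 says the DSMP will adhere to the protocol. That favours the protocol rule but does not tell a reader of section 5 to disregard the sentence there.

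**2. Visits lost**

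Inputs: 40 randomised participants (protocol 9.2.1); SAFTEE, PHQ-9 and NAS after baseline at weeks 5, 10 and 18 (protocol Table 3). The week 14 yoga-only interview carries none of these measures and is not counted.

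- Scheduled post-baseline visits: 40 × 3 = 120.
- Loss per event: 3 of 3 if before week 5, 2 of 3 if between weeks 5 and 10, 1 of 3 if after week 10.
- One event: 1/120 to 3/120 = 0.8% to 2.5%.
- Two events: 2/120 to 6/120 = 1.7% to 5.0%.

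The range of 0 to 2 events is an assumption, since the documents give no rate. Over it, the loss is 0 to 6 of 120 visits (0% to 5.0%). This is an upper bound: it supposes that the participant would otherwise have completed every remaining visit. Some would decline, or be removed under the risk rule.

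**3. Retention targets** (target outcomes table, protocol 9.5.1)

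- Week 10: 0.80 × 40 = 32 completers needed, so 40 − 32 = 8 losses allowed. Two events use at most 2/8 = 25% of that allowance.
- Week 18: 0.70 × 40 = 28 needed, so 40 − 28 = 12 allowed. Two events use at most 2/12 = 16.7%.
- Each event costs 1/40 = 2.5 percentage points; two cost 5.0.

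Neither target would be missed from this cause alone.

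**4. What is kept in any case**

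- Inpatient hospitalisation is a serious adverse event by definition (protocol 7.4). The research assistant records dates, severity and healthcare contacts (protocol 9.1.2).
- Related serious events are followed until resolution or stabilisation (protocol 7.4 and 7.6), and halt the intervention pending review (protocol 9.4.2, DSMP 3.5).
- Expected or unrelated serious events are reviewed per occurrence by the principal investigators and semi-annually by the safety monitoring committee (DSMP 7.8).
- Data collected before the event stay in the analysis (protocol 9.3).

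What is exposed is mainly the later routine inquiry after an event judged unrelated.

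**The case against.** The strongest reply is that the protocol already settles the matter: three sections continue assessments, and the DSMP undertakes to follow the protocol. On that view only an unusually literal reader would stop the visits. Nor is a study-level exit foreign to the protocol. Section 7.1 allows removal when participation raises risk, and the DSMP sentence could be a stricter, automatic form of that safeguard. Whether exit should be automatic or case by case is partly a clinical choice.

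Much of this stands, and it keeps the priority low. It does not remove the conflict. The DSMP sentence is mandatory, it follows directly on one about continuing in the study, and section 9.5.1 applies to everyone enrolled.

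Three further inferences go beyond the documents:

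- *A hospital stay need not cost a visit, because procedures already exist.* Only late collection is general: "RAs will still collect data if possible even if it is later than that two-week window". The telephone and off-site provisions are written for released participants. For them, "we will complete the follow-up assessment in person in our offices at Brown University or in the facility where the participant is located" applies, and the facility option needs that facility's approval.
- *The event will hardly occur, because observation in prison replaces hospitalisation.* DSMP section 5 lists psychiatric observation among the standard procedures, if needed; it does not rule out hospital. It calls release during the study unlikely, but eligibility requires only 90 days remaining against 18 × 7 = 126 days of follow-up. Suicide risk is, however, a screening exclusion, so few events are expected.
- *The DSMP sentence is the only text to change.* A reworded sentence would still require the intervention to stop, on a trigger that protocol section 8 does not list.

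**Conclusion.** The conflict holds: one DSMP sentence prescribes study exit where the protocol prescribes continued assessment of willing participants. Followed as written, it would drop PHQ-9, SAFTEE and NAS visits for a reason plausibly tied to outcome and safety.

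A reader might infer that the sentence threatens the retention benchmarks or hides a serious safety event. The documents support neither. Under the assumed event range the allowances at weeks 10 and 18 are not exhausted, and the event is recorded and reviewed whether or not later visits take place. The clinical outcomes are also exploratory in this pilot.

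Confidence is high that the wording conflicts. It is lower for the consequence, which depends on an unknown event rate, on participants' willingness to continue, and on staff following the DSMP sentence rather than the protocol. This is an optional improvement.

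**What to change.** Change the DSMP section 5 sentence so that these participants *will be discontinued from the study intervention; outcome and AE assessments continue on the usual schedule if the participant is willing and it is clinically appropriate*. Add hospitalisation due to concerns about suicidality to the list in protocol section 8, so that the two documents match. Leave the risk-based removal rule in protocol 7.1 and DSMP 5 unchanged.

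The cost is a minor document change. Under DSMP section 2, protocol amendments that are not minor administrative changes go to the independent monitor, then NCCIH, then the IRB, so the section 8 addition may need that route. There is also some effort in following a vulnerable participant. Late collection is already allowed, but collection by telephone or in person during a hospital stay should be planned on the basis that the facility must approve it.
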